## **II Purpose of Research**

This project aims to build a mobile health supportive care program for family caregivers with dementia combined with diabetes, and to evaluate the clinical application effect of the mobile health supportive care program for family caregivers with dementia combined with diabetes. The research results will provide more economical and efficient care guidance for family caregivers, thus improving the overall quality of care and quality of life for patients with dementia and diabetes.

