## **III Research Method**

### **(1) Object of Study**

#### **1) Source of the study subjects and the sampling methods**

The convenience sampling method started from May 2022 to the end of the sample number, and family caregivers with dementia and diabetes in 5 community neighborhood committees (cities) and 10 villages (rural areas) of a community health service center that met the inclusion criteria were selected.

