### **4) Sample size estimation**

The sample size is calculated according to the ratio of 1:1 between the test group and the control group, and the sample size calculation method of "difference test of two sample means comparison" is used.

The calculation formula is:

$$n_1=n_2=2\left[\frac{(\mu_{\alpha}+\mu_{\beta})}{\delta/\sigma}\right]^2 + \frac{1}{4}\mu^2$$

Based on the literature review, with the caregiver care burden as the main outcome measure of this study,  $n_1$  and  $n_2$  were the required sample size, respectively;  $\alpha = 0.05$ ,  $\beta = 0.1$ , two-sided test,  $\mu_0.05/2=1.96$ ,  $\mu_0.1=0.282$ , mean difference  $\delta = 33.91-27.04=6.87$ , and overall standard deviation of the intervention  $\sigma = 6.85$ . After calculation, the sample size of both groups was 22 cases, considering 15% shedding

rate, at least 26 cases in each group, a total of 52 cases. Finally, 30 patients were included in each group, totaling 60 patients.

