### **(3) Data Processing and Statistical Analysis**

Statistical data was analyzed using SPSS 25.0 software. Quantitative data were represented by normal distribution ( $\pm s$ ), non-normal by M (QR); qualitative data by n (%). Quantitative data is designed to compare two independent samples. If sample data follows normality, independent sample t-test is used, otherwise Mann Whitney U test is used; for comparison before and after intervention; if the difference follows normal distribution, paired t-test is used, otherwise Wilcoxon rank sum test is used. To compare qualitative data between different groups, use  $\chi^2$  test or Fisher's exact test; compare rank data between different groups. Subject analysis (Per-protocol Subjects Analysis, PP).

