## **四、The Project Involves the Implementation Plan of the Ethical Part**

- Study subjects, number of cases, intervention methods, enrollment criteria, and exclusion criteria

There were 60 elderly family caregivers with dementia and diabetes, and the intervention method was mobile medical supportive care program. The enrollment criteria were: ① Care nannies and hourly workers with legal kinship (such as spouse, children or siblings), etc.; ② worked for 8 hours / day and 5 days / week for 1 month; ③ well-aware

and reading and understanding adults; ④ has at least a smart phone (Internet access) and skilled use; ⑤ informed consent and voluntary participation in research. Exclusion criteria: ① Severe physical or mental illness; ② patients with drug or alcohol dependence; ③ caregivers are participating in similar intervention studies.

- Specimens to be collected and the sources of the specimens

No specimens were collected

- Recruitment and protection measures of the subjects

① Recruitment: Select family caregivers of elderly people with dementia and diabetes in 5 community neighborhood committees (cities) and 10 natural villages (rural areas) in the jurisdiction of a community health service center that meet the exclusion criteria.

② Protection: Carers have the right to refuse to answer any items that cause psychological discomfort and provide door-to-door assessment services whenever possible.

- Research risks and preventive measures

No medication or any radioactivity, invasive procedures, and in principle will not cause any risk or adverse effects on the physical health of the subject.

- The benefit of the study

Participation in this study may help subjects to better understand the health of their caregivers, and the intervention is expected to improve their social support function and reduce their care burden and poor mood. However, it is also possible that participation in this study did not directly benefit the subjects.

- Exps and compensation for subjects' participation in the project

Throughout the study, the subjects were unpaid and no fees were charged to the subjects. When the subject is injured by his participation in this study, the necessary medical measures will be taken for treatment and compensation will be paid in accordance with the current national laws. If in this study, lost work or transportation expenses, reasonable expenses will be compensated.

- Information and confidentiality about the subjects

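### Per-protocol, without a definition, is the only analysis set named in the supplied text, so measured caregivers could be left out of the burden comparison after allocation

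*Combined protocol and SAP*

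**What the plan says.** Section III (3), Data Processing and Statistical Analysis, is the whole statistical plan. It lists software, descriptive summaries and tests, and ends with "Subject analysis (Per-protocol Subjects Analysis, PP". It gives no adherence threshold, deviation rule or required assessments for that set, and no time at which membership is fixed. The clause just before it, "compare rank data between different groups", has no test attached, so words may have been lost at this spot.

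Other sections bear on the point:

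- Section III (1) 4), Sample size estimation, sizes the trial "with the caregiver care burden as the main outcome measure of this study". It enlarges the sample after "considering 15% shedding" and plans 30 per group.
- Section II sets the aim: to "evaluate the clinical application effect of the mobile health supportive care program" for family caregivers.
- The ethical section states that "Carers have the right to refuse to answer any items that cause psychological discomfort", so partly completed forms can occur. Under the same protection measure it offers to "provide door-to-door assessment services whenever possible".
- No supplied section names an all-allocated set or says how missing CBI scores are handled.

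**The concern.** Per-protocol is named for the analysis as a whole, so it applies to burden because burden is the main outcome. If membership depends on following the programme, caregivers with a final CBI can be removed after allocation. The programme is the only intervention that the text describes, so removal for non-use would probably fall mainly in the test group. If those removed carry more burden than those kept, the programme looks better than it is. If they carry less, it looks worse. With no criteria written down, membership could also be settled after scores are known.

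There is a mismatch of question as well. A comparison limited to caregivers who complied does not describe the programme's effect in the caregivers it is offered to, which is the aim in section II.

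Two groups must be kept apart: measured caregivers who did not adhere, whom the choice of set removes, and caregivers with no final CBI, whom no choice of set can bring back.

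**Working it through.** **The plan's own figure.** Inputs from Sample size estimation: difference 33.91 − 27.04 = 6.87, SD 6.85, two-sided 5%, 90% power. The formula gives 2 × [(1.96 + 1.282) × 6.85/6.87]² + 1.96²/4 = 20.90 + 0.96 = 21.86, so 22 per group. Then 22/0.85 = 25.9, so 26. Both stated sizes reproduce if the printed 0.282 is read as 1.282. That is a separate matter and does not affect this point.

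**False difference from removal (assumed inputs).** No true effect, n = 30 per arm, SD 6.85. In each arm, k caregivers are removed according to a latent variable with correlation r to the final score. The mean of those kept shifts by r × SD × S(k)/(n − k), where S(k) is the expected sum of the k largest of 30 standard normal values: S(4) = 6.20, S(2) = 3.66. Type I error comes from simulation with a two-sided t-test; repeat runs differ by about 0.2 percentage points.

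| Removed, arm 1 / arm 2 | r | False difference (points) | Share of 6.87 | Type I error |
|---|---|---|---|---|
| 4 / 0 | 0 | 0 | 0% | 5.0% |
| 4 / 4, same r | 0.5 | 0 | 0% | 5.7% |
| 4 / 2 | 0.3 | 0.3 × 6.85 × (6.20/26 − 3.66/28) = 0.22 | 3% | 5.3% |
| 4 / 2 | 0.5 | 0.5 × 6.85 × (6.20/26 − 3.66/28) = 0.37 | 5% | 6.1% |
| 4 / 0 | 0.3 | 0.3 × 6.85 × 6.20/26 = 0.49 | 7% | about 6% |
| 4 / 0 | 0.5 | 0.5 × 6.85 × 6.20/26 = 0.82 | 12% | 7.6% |

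A negative r gives the same size in the opposite direction.

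**How strong is the last row?** The gap between removed and kept caregivers is 0.5 × 6.85 × (6.20/4 + 6.20/26) = 6.1 points, nearly the whole planned effect, and all removals fall in one arm.

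**What a change of set repairs (4 / 0, r = 0.5).**

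- All 4 measured: the false difference falls from 0.82 to 0.00, with type I error 5.0%.
- 2 measured and 2 without a final CBI: 0.38 remains.
- None measured: all of the 0.82 remains. A baseline-adjusted comparison then leaves 0.62 or 0.43 (baseline-final correlation 0.5 or 0.7) if loss follows the final score, and 0.00 if loss depends on baseline burden only.

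**Power of an all-allocated comparison (noncentral t, SD 6.85).** Suppose 15% of the test group gain nothing; the difference becomes 0.85 × 6.87 = 5.84. Since 15% of 30 is 4.5, a 15% loss leaves 25 or 26 per group.

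| Measured per group | Difference 6.87 | Difference 5.84 |
|---|---|---|
| 30 | 96.9% | 90.1% |
| 26 | 94.4% | 85.4% |
| 25 | 93.5% | 84.0% |

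The 84% to 85% figures use 15% twice: once for caregivers who are measured but gain nothing, and again for a separate loss in each group. If the lost caregivers are the non-adherers, the measured difference is undiluted and power is about 94%. If mixing also widens the test-group SD, its variance is 6.85² + 0.15 × 0.85 × 6.87² = 52.9. The pooled SD is then √[(46.9 + 52.9)/2] = 7.07, and power with 30 per group is 88.2% instead of 90.1%.

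**The case against.** The strongest reply is that the evidence is one broken sentence. Translation or extraction may have dropped words, and the source-language plan may contain an all-allocated set. That stands as a limit: the point concerns the supplied text, and a reader should not infer that the sponsor decided against an all-allocated analysis. It does not remove the point, because nothing marks the line as blacked out and no other section supplies the missing set or definition.

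Second, per-protocol may simply mean completers here. If so, no measured caregiver is dropped and only missing data remain. The text does not settle this, which is a reason to define the set.

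Third, a reader might take the 7.6% error rate as what to expect. The documents do not support that. They give no rate of non-adherence, no loss by arm and no link between loss and burden. The 15% is an allowance for loss, not for non-adherence. Milder assumptions give 0.2 to 0.5 points.

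Fourth, a reader might infer that the permission to refuse items, with no scoring rule, undermines the result. It shows that partial forms are foreseeable, but nothing in the documents says how many there will be or how they relate to burden.

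Finally, no allocation method is described. The section on source and sampling says only "The convenience sampling method started from May 2022", and the sample-size section gives a 1:1 ratio. Analysing everyone as allocated therefore cannot be presented as restoring a randomised comparison.

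**Conclusion.** The point holds as a gap in the stated analysis set. As written, the plan allows measured caregivers to be left out of the main comparison after allocation, by criteria that it does not state, and that comparison does not match its own aim.

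The likely bias is modest and its direction unknown: zero if removal is unrelated to burden or is equal and similarly driven in both arms, and about 0.2 to 0.8 points in the unbalanced cases shown. All of this rests on assumed numbers removed and assumed correlations; only the SD, the 30 per arm and the planned 6.87 come from the plan.

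The sample size is not called into question. Nor do the documents support saying that an all-allocated analysis would leave the trial short of power: a fall to 84% to 85% needs dilution and a further, separate loss together.

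This should be fixed because a better primary set costs little. Confidence is medium, given the damaged sentence.

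**What to change.** Replace the fragment in section III (3) with: *The primary CBI analysis includes all allocated caregivers with a final CBI, in their assigned group, regardless of programme use; per-protocol, with criteria fixed before outcomes are seen, is a sensitivity analysis.* If the source-language plan already has such a set, restore it in the text.

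For missing final scores, use the baseline CBI in an adjusted comparison, provided it is collected, as the planned before-and-after comparison implies. Multiple imputation is optional. Report the numbers and reasons for loss by group.

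Limits: the change of set does nothing for caregivers without a final CBI, adjustment corrects only selection explained by baseline, and neither makes the groups comparable while allocation is undescribed.

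Cost: wording and a little extra analysis. The estimate may be diluted by caregivers who made little use of the programme. With 15% gaining nothing and all 30 per group measured, power stays at about 90%.

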## **四、The Project Involves the Implementation Plan of the Ethical Part**

- Study subjects, number of cases, intervention methods, enrollment criteria, and exclusion criteria

There were 60 elderly family caregivers with dementia and diabetes, and the intervention method was mobile medical supportive care program. The enrollment criteria were: ① Care nannies and hourly workers with legal kinship (such as spouse, children or siblings), etc.; ② worked for 8 hours / day and 5 days / week for 1 month; ③ well-aware

and reading and understanding adults; ④ has at least a smart phone (Internet access) and skilled use; ⑤ informed consent and voluntary participation in research. Exclusion criteria: ① Severe physical or mental illness; ② patients with drug or alcohol dependence; ③ caregivers are participating in similar intervention studies.

- Specimens to be collected and the sources of the specimens

No specimens were collected

- Recruitment and protection measures of the subjects

① Recruitment: Select family caregivers of elderly people with dementia and diabetes in 5 community neighborhood committees (cities) and 10 natural villages (rural areas) in the jurisdiction of a community health service center that meet the exclusion criteria.

② Protection: Carers have the right to refuse to answer any items that cause psychological discomfort and provide door-to-door assessment services whenever possible.

- Research risks and preventive measures

No medication or any radioactivity, invasive procedures, and in principle will not cause any risk or adverse effects on the physical health of the subject.

- The benefit of the study

Participation in this study may help subjects to better understand the health of their caregivers, and the intervention is expected to improve their social support function and reduce their care burden and poor mood. However, it is also possible that participation in this study did not directly benefit the subjects.

- Exps and compensation for subjects' participation in the project

Throughout the study, the subjects were unpaid and no fees were charged to the subjects. When the subject is injured by his participation in this study, the necessary medical measures will be taken for treatment and compensation will be paid in accordance with the current national laws. If in this study, lost work or transportation expenses, reasonable expenses will be compensated.

- Information and confidentiality about the subjects

All information concerning the subject's personal privacy will be kept strictly confidential and only for academic purposes, and will not be disclosed by any public report of the results of this study. This information will not be available if necessary except for the ethics committee and relevant researchers.

- Process and procedure for the signing of the informed consent form

① Designated a member of the research group to explain the purpose, significance and research process of the study to the subjects and their caregivers (legal guardian or legal representative), do a good job in communication and coordination, gain their trust, establish a good cooperative relationship and sign the informed consent form.

② On the principle of the subject to sign together, the investigator and the subject to sign together. For adult subjects who are capable and able to identify themselves and are not illiterate, the legal representative or the legal representative may sign the informed consent, for subjects without capacity, incompetent, unconscious or illiterate to give informed consent, after the oral consent, the witness signed the informed consent on the informed consent form.

③ After recruitment, 20% of the subjects were selected from the population and asked whether they were informed of the study and the content of the informed consent.

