#### **2) Inclusion criteria for the study subjects**

Caregivers:

- Carers have legal kinship with the patient (such as spouse, children, or siblings), nannies and hourly workers who do not charge care fees;
- work 8 hours / day and 5 days / week for 1 month;
- aware, reading and understanding adults;
- has at least one smart phone (access to Internet) and skilled use;

- informed consent and voluntary participation in investigation and research.

Care recipients:

- meets the diagnostic criteria for senile dementia;
- meets the diagnostic criteria for type 2 diabetes;
- patients are 60 years old and the resident population in the area.

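### Do the two versions of the caregiver eligibility criteria leave it unclear who may enter the trial?

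*Combined protocol and SAP*

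**What the plan says.** Eligibility is described in two places.

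- **Section III (1), Object of Study.** The sampling paragraph takes family caregivers "of a community health service center that met the inclusion criteria were selected". The first caregiver inclusion criterion reads "Carers have legal kinship with the patient (such as spouse, children, or siblings), nannies and hourly workers who do not charge care fees". Four further caregiver criteria follow (hours worked, capacity to read and understand, smartphone use, consent). There are also care-recipient inclusion criteria, three caregiver exclusions and two care-recipient exclusions.
- **Section IV (headed 四), the ethics implementation plan.** It opens with "There were 60 elderly family caregivers with dementia and diabetes" and gives the first caregiver criterion as "Care nannies and hourly workers with legal kinship (such as spouse, children or siblings), etc". The no-fee condition is absent. The recruitment item covers the same 5 neighbourhood committees and 10 villages and selects caregivers "in the jurisdiction of a community health service center that meet the exclusion criteria".

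Neither section refers to the other, and the text supplied does not say which takes precedence. The aim in Section II is to "evaluate the clinical application effect of the mobile health supportive care program for family caregivers with dementia combined with diabetes". The only analysis population named, in Section III (3), is "Subject analysis (Per-protocol Subjects Analysis, PP"), and it is not defined. Section III (1) 4) plans "at least 26 cases in each group, a total of 52 cases. Finally, 30 patients were included in each group".

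**The concern.** Two eligibility lists that disagree are normally worth stopping over. Read literally, Section III lets in unpaid nannies and hourly workers who are not relatives, while Section IV requires kinship of them. The aim speaks of family caregivers, so admitting unrelated helpers bears on whom the result describes.

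The analysis could be affected too. If the per-protocol set requires that participants met the eligibility criteria, an unrelated helper would be analysed under one list and dropped under the other, possibly after outcomes were known. With 30 per group, each such person is 1/30 = 3.3% of a group and 1/60 = 1.7% of the trial. Enough removals would use up the margin over the planned minimum. A recruitment sentence that selects on the exclusion criteria adds to the impression that the rules were not controlled.

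**Working it through.** **1. How far the two lists differ**

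| Item | Section III | Section IV | Agree in substance? |
|---|---|---|---|
| Caregiver inclusion 1 | Kin, then helpers charging no fee | Helpers, with kinship attached to them, *etc.*; no fee condition | No |
| Caregiver inclusion 2 to 5 | Hours, capacity, smartphone, consent | Same | Yes |
| Caregiver exclusions (3) | Illness, dependence, similar study | Same | Yes |
| Care-recipient criteria | Dementia, type 2 diabetes, age, residence, and two exclusions | None given | Omitted from IV |
| Recruitment rule | Meets *inclusion* criteria | Meets *exclusion* criteria | One word differs |

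The substantive difference is 1 of 5 caregiver inclusion criteria and 0 of 3 caregiver exclusions.

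**2. Whether the literal reading of Section IV can be meant**

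Taken word for word, its first criterion admits only nannies and hourly workers who are the patient's spouse, child or sibling. A wife or son who is not also a nanny would be ineligible, in a section whose first sentence calls the participants family caregivers. That sentence has the same looseness: read literally, "There were 60 elderly family caregivers with dementia and diabetes" gives the caregivers the patients' diseases. Text of this kind cannot carry an argument that depends on which noun a qualifier attaches to. The closing *etc.* leaves the list open in any case.

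Section III is not perfectly clear either. Its grammar does not quite settle whether unpaid helpers are a separate group or must also be kin, or whether the no-fee condition reaches relatives. The ordinary reading is a list: kin, plus helpers who are not paid.

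**3. Whether the inverted recruitment sentence could be acted on**

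Section IV labels its enrolment and exclusion criteria correctly a few lines earlier, and Section III states the rule the right way round for the same sites. Nobody would recruit only people with severe illness, substance dependence or enrolment in another such study.

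**4. The plan's sample size, reproduced**

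Inputs from Section III (1) 4): difference 6.87, SD 6.85, two-sided α = 0.05 (u = 1.96), β = 0.1, loss 15%. The normal deviate for β is printed as 0.282; the stated result needs 1.282.

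- 2 × [(1.96 + 1.282) / (6.87/6.85)]² + 1.96²/4 = 20.90 + 0.96 = 21.86, so 22 per group, as stated.
- 22 / (1 − 0.15) = 25.9, so 26 per group, as stated.
- The printed 0.282 would give 9.99 + 0.96 = 10.96, or 11 per group, so it is a misprint with no consequence.

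None of these figures depends on the wording of the caregiver criterion.

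**5. The unfavourable case**

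- Spare places per group: 30 − 26 = 4.
- Four removals: 26 × 0.85 = 22.1, still at the required 22.
- Five removals: 25 × 0.85 = 21.25, about 21.
- Power of a two-sided t-test with difference 6.87 and SD 6.85: 90.1% at 22 per group, 88.7% at 21.

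The loss is 1.4 percentage points. To get there, one group must contain five unrelated, unpaid nannies or hourly workers, each meeting the hours criterion of 8 hours a day, 5 days a week. All five must then be removed, with the full 15% loss on top. The documents give no counts by caregiver type, and nothing suggests that five such people exist.

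**The case for a change.** The strongest case for acting is that the public text is all a reader has, and it does not say with certainty whether an unrelated unpaid helper is eligible. Section III is itself ambiguous, Section IV restates eligibility as a list of its own, and correcting the words would cost almost nothing. An aim framed around family caregivers sits a little awkwardly with admitting people who are not family.

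The wording difference and the residual ambiguity stand. The consequence drawn from them does not. The eligibility choice belongs to the sponsor under any wording, and Section III gives a workable rule to recruit by. If some participants turn out to be unrelated, a baseline description shows it. The General Data questionnaire in Section III (2) may already record relationship, but its items are not shown, so neither presence nor absence can be claimed.

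The worry about removal after outcomes are known comes from the undefined per-protocol set. It would remain if the two lists matched word for word, and it also assumes a definition that the plan does not give. It is a separate matter and does not make this one larger.

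**Conclusion.** No change to the plan follows. Section IV is an abridged and poorly worded restatement of Section III, and *exclusion* in its recruitment sentence is a slip for *inclusion*. Anyone running or analysing the trial would take eligibility from Section III, where the study population is defined and where alone the care-recipient criteria appear. Doing so leaves the sample size, the planned tests and the conclusion as they are.

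The size is 1 of 5 caregiver inclusion criteria plus one word, with no demonstrated effect on power. Even the contrived five-removal case costs about 1.4 percentage points.

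This rests on two assumptions: that Section III is read as the operative list, and that unrelated unpaid helpers meeting the hours criterion are few, which the documents neither confirm nor contradict. The absence of a precedence statement is confirmed only for the text available, since some opening material was removed.
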